Official Title: Determination of Metabolomic Profile Differences in Sarcopenia Accompanying Fibromyalgia Syndrome

NCT Number: Not yet assigned (Initial Submission)

Document Date: Jan 25, 2023

STUDY PROTOCOL AND STATISTICAL ANALYSIS PLAN

This study was conducted in a single-center, cross-sectional observational design. The study complied with the Declaration of Helsinki and was approved by the Ankara Bilkent City Hospital No. 2 Clinical Research Ethics Committee with the number E2-22-1740. Informed consent was obtained from all individual participants included in the study. This study included 44 female patients aged 18-60 who were diagnosed with fibromyalgia according to the ACR (American College of Rheumatology) 2016 diagnostic criteria and applied to Ankara Bilkent City Hospital Physical Therapy and Rehabilitation Hospital outpatient clinics between May 2022 and December 2022 and 22 female healthy controls. Female volunteers who applied to Ankara Bilkent City Hospital Physical Therapy and Rehabilitation Hospital outpatient clinics for other reasons and who did not have any accompanying diseases such as fibromyalgia and sarcopenia constituted the healthy controls. Exclusion criteria include cognitive dysfunction; history of serious cardiac disease, COPD (Chronic Obstructive Pulmonary Disease), epilepsy, malignancy, neuromuscular disease, inflammatory rheumatic disease, endocrine disease and organ failure; currently pregnant; use of systemic glucocorticoid, ACE inhibitor, angiotensin receptor blocker, statin, sulfonylurea; male gender. Fibromyalgia is more common in women. Gender differences may affect metabolome results. That's why all participants in the study were women.

Demographic data, medication use and disease duration of the participants were recorded. Patients with fibromyalgia and healthy volunteers were screened for sarcopenia by using hand grip strength measurement with a hand dynamometer, muscle mass measurement

with bioimpedance analysis. According to EWGSOP2 (European Working Group on Sarcopenia in Older People) criteria, patients with hand grip strength below 16 kg were considered to have probable sarcopenia. 22 participants were included in the FMS PS- (Fibromyalgia Syndrome without Probable Sarcopenia) group and 22 participants were included in FMS PS+ (Fibromyalgia Syndrome with Probable Sarcopenia) group. The hand grip strength of all individuals in the healthy control group was over 16 kg.

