Plasma samples were collected from all participants. Samples were centrifuged at 1500 rpm for 10 minutes and stored at -80 degrees to be used in metabolome analysis.

Measurement of plasma metabolomics

A mixture of methanol/water (90%:10% v/v) was added onto 100 μ L of plasma. The samples were kept at -20°C overnight. The obtained samples were centrifuged at 15000 rpm for 10 minutes. Proteins precipitated and metabolites remained in the methanol/water mixture. The resulting metabolite mixture was placed in a vacuum centrifuge to remove methanol and water. 20 μ L methoxyamine (20mg/20 μ L) was added to the resulting metabolites. Afterwards, the samples obtained after derivatization with 80 μ L MSTFA + 1% TMCS were analyzed by gas chromatography/mass spectroscopy (GC/MS).

Schimadzu qp2010 device was used in the analyses. In this study, FAME mix standards were used as standards in the system. DB-5MS stationary phase column (30 m+10m DuraGuard x 0.25mm i.d. and 0.25- μ m) was used in the analysis. The oven temperature was fixed at 70°C for one minute, then increased to 320°C in increments of 10 degrees per minute and remained for 10 minutes. Afterwards, the system returned to its original temperature. The analysis took a total of 37 minutes. In the GC/MS system, the scanning range was 50-600 m/z.

The obtained GC/MS data were evaluated on the MS-DIAL metabolomics platform. Untargeted metabolomics studies have been conducted. Metabolites with a match score of 70

and above were accepted using the Kovats retention index database. In the pre-data analysis processes within the MS DIAL platform, peak identification, deconvolution and data alignment processes were primarily carried out. Subsequently, the structures of the metabolites were elucidated. Peak areas and heights were used in semi-quantitative analysis. Normalization processes were also carried out according to the total ion chromatogram. Two-tailed t-test was performed between experimental groups and significantly changed metabolites were identified. Metaboanalyst 4.0 platform and KEGG (Kyoto Encyclopedia of Genes and Genomes) database were used in pathway analyses.

Statistical Analysis

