SPSS (Statistical Package for Social Sciences) 22.0 Statistical Package Program and MS-DIAL metabolomics platform were used to evaluate the data. After determining whether the data showed normal distribution, statistical evaluation was made with appropriate parametric or non-parametric tests. The numerical data obtained are given as mean and standard deviation, and categorical data are given as number (n) and percentage (%). Descriptive statistical methods (Mean, Standard deviation, upper and lower values) were used when evaluating the data. After comparing the metabolome data between the three groups, cluster analysis was performed and pathway differences between the groups were revealed. The results were evaluated at the 95% confidence interval and the significance level was $p<0.05$.

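### Untargeted metabolite screen: metabolites are called significantly changed on t-tests at p<0.05, with no multiplicity control or exploratory label, so the false share of the list is uncontrolled

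*Combined protocol and SAP*

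**What the plan says.** The section on measurement of plasma metabolomics describes the assay as untargeted: "Untargeted metabolomics studies have been conducted". Features enter the screen through an identification filter ("Metabolites with a match score of 70" or above, against a retention-index database). The test follows: "Two-tailed t-test was performed between experimental groups and significantly changed metabolites were identified". Pathway work comes next: "Metaboanalyst 4.0 platform and KEGG (Kyoto Encyclopedia of Genes and Genomes) database were used in pathway analyses".

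The Statistical Analysis section gives one level for everything: "The results were evaluated at the 95% confidence interval and the significance level was $p<0.05". It also says that, after a normality check, "statistical evaluation was made with appropriate parametric or non-parametric tests", and: "After comparing the metabolome data between the three groups, cluster analysis was performed and pathway differences between the groups were revealed".

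The document does not state:
- how many metabolites were tested;
- which pairwise contrasts were run;
- whether a three-group test had to be significant before the pairwise tests;
- any adjustment for multiple testing, any q-value or any validation set;
- whether the list of changed metabolites is the input to the pathway analysis;
- that the screen is exploratory.

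**The concern.** The official title is "Determination of Metabolomic Profile Differences in Sarcopenia Accompanying Fibromyalgia Syndrome", so the list of differing metabolites is a main output of the study. A 5% level per test limits the error of one comparison. It says nothing about the composition of a list picked from many comparisons because each passed that level. The match-score cut-off does not help, because it filters identification and not statistical error.

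No treatment decision or sample size rests on the list. What is at stake is how it can be read: it is presented as a set of established changes, and a reader cannot tell from p<0.05 how much of it is noise. If the same list feeds the pathway step, which is not stated, the uncertainty carries over to the pathways.

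**Working it through.** The document gives no power, error-rate or false-discovery figure to reproduce. The check therefore works out what the stated rule implies.

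**Inputs from the document.** 22 per group in three groups; two-tailed t-test (df = 22 + 22 − 2 = 42); level 0.05.

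**Assumptions, not in the document.** Number of metabolites M = 50, 100 or 200; share truly changed π = 5% to 50%; standardised difference d = 0.3 to 1.0.

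**1. No metabolite truly differs, one contrast.** Expected false positives = 0.05 × M. With independent tests, the chance of at least one = 1 − 0.95^M. The correlated column is a simulation with correlation 0.5 in blocks of 10.

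| M | Expected false positives | Chance of ≥1, independent | Chance of ≥1, correlated |
|---|---|---|---|
| 50 | 2.5 | 92% | 82% |
| 100 | 5 | 99.4% | 97% |
| 200 | 10 | >99.9% | 99.9% |

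Correlation lowers the chance of any false positive but leaves the expected number unchanged.

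**2. Three groups.** Suppose all three pairwise t-tests are run without a gate. By simulation, a null metabolite is then flagged at least once about 12% of the time, which is about 6, 12 and 25 metabolites at the three values of M. A significant one-way ANOVA required first brings this to about 5%, which still leaves 2.5, 5 and 10. A gate therefore limits error across contrasts for one metabolite, but not across metabolites.

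**3. Some metabolites truly differ.** False share = 0.05(1 − π) / [0.05(1 − π) + power × π]. Power from the noncentral t at 22 per group is 0.163, 0.367, 0.736 and 0.900 for d = 0.3, 0.5, 0.8 and 1.0. Example with d = 0.8 and π = 0.10: 0.05 × 0.90 = 0.045; 0.736 × 0.10 = 0.0736; 0.045 / 0.1186 = 0.38.

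| d | π = 50% | 20% | 10% | 5% |
|---|---|---|---|---|
| 0.3 | 23% | 55% | 73% | 85% |
| 0.5 | 12% | 35% | 55% | 72% |
| 0.8 | 6% | 21% | 38% | 56% |
| 1.0 | 5% | 18% | 33% | 51% |

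This formula does not involve M. It is a ratio of expected counts; the simulated mean false share at M = 100 is slightly lower (37% against 38% in the example).

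**4. Effect of Benjamini-Hochberg (BH).** Simulation with M = 100, π = 10%, independent tests, one contrast:

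| d | Rule | Power | Mean false share | List empty |
|---|---|---|---|---|
| 0.5 | raw p<0.05 | 0.37 | 54% | – |
| 0.5 | q<0.05 | 0.03 | 4% | 72% |
| 0.5 | q<0.20 | 0.12 | 18% | 37% |
| 0.8 | raw p<0.05 | 0.74 | 37% | – |
| 0.8 | q<0.05 | 0.27 | 4% | 14% |
| 0.8 | q<0.10 | 0.39 | 9% | 5% |
| 0.8 | q<0.20 | 0.54 | 18% | 1% |
| 1.0 | raw p<0.05 | 0.90 | 32% | – |
| 1.0 | q<0.05 | 0.58 | 5% | 1% |

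With correlated metabolites and the 10 true ones in one block, q<0.05 leaves the list empty in about 80%, 40% and 15% of runs at d = 0.5, 0.8 and 1.0. When no metabolite differs, BH at q<0.05 puts anything on the list in about 5% of correlated runs, against 82% to 99.9% for raw p<0.05.

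**The case against.** **This is discovery work.** The study is a single-centre, cross-sectional comparison with no stated primary endpoint or formal hypothesis, and readers in the field take an untargeted assay as a sign of exploration. But the word describes the assay, not the status of the results, which are reported as significant without a caveat.

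**The evidence is silence in a short document.** A correction may have been applied inside the software, and the 0.05 level is given for the results in general and not specifically for the t-tests. This stands as a limit: what is shown is that no control is stated. Applying 0.05 to the t-tests is the natural reading, since no other level appears. If an adjustment was made, one sentence naming it would settle the point.

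**The metabolite count is assumed.** Only identified metabolites were tested, so M could be below 50. With the same correlation model, the chance of at least one false positive is about 63% at M = 30 and about 50% at M = 20. The figures move, but the conclusion does not.

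**The false share might be small.** With half the metabolites truly changed and d = 0.8 it is only 6%. This is correct: the calculation shows that the share is unknown and unbounded by any stated rule, not that it is high.

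**Correction costs power at 22 per group.** This stands too, and is the reason to keep raw p-values in view under an exploratory label.

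**Conclusion.** The concern holds. As written, the plan turns an untargeted screen into a list of significant metabolites with no stated control over how many entries are false, and without calling the screen exploratory. If nothing truly differed, the rule would still very likely produce a list: 82% to over 99% for 50 to 200 metabolites in one contrast. If some metabolites differ, the false share could be anywhere from about 5% to 85% for d = 0.3 to 1.0 and 50% to 95% true nulls. These sizes depend on the assumed M, d and π; the absence of a stated bound does not. Because the list is a main output and the repair is cheap, it should be corrected before any metabolite is reported as significantly changed. The consequence for the pathway results is conditional on an input that the document does not state.

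**What to change.** 1. Report the number of metabolites tested, the contrasts run, and whether a three-group test gated them.
2. Settle which p-values are used. The metabolomics section names a t-test, while the Statistical Analysis section allows parametric or non-parametric tests. q-values can properly be added afterwards, but they are only as sound as the p-values beneath them.
3. Compute BH q-values across all accepted metabolites within each contrast, and report raw p and q for every metabolite. Per-contrast BH does not set one error rate across contrasts, and the report should say so.
4. Reserve the claim of significant change for metabolites meeting a stated FDR level, for example q<0.05. Label those with only raw p<0.05 as exploratory.
5. State which list feeds the pathway analysis. If the FDR list is short or empty, use a whole-profile enrichment method or label the pathway results exploratory.
6. Optionally, present fibromyalgia with against without probable sarcopenia as the main contrast, since it matches the title. Recruitment and analysis are described in the past tense, so this choice, and any q level looser than 0.05, should be labelled post hoc.

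**Cost.** Reporting text and one column of q-values on existing data. The price is fewer discoveries: at d = 0.8 in the simulated setting, power falls from 0.74 to 0.27 at q<0.05, and at d = 0.5 the list would usually be empty. A looser stated level recovers some power but admits more false entries.

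### Metabolites are selected by unadjusted t-tests between non-randomised groups although age and medication data are recorded, so an age or drug difference could be read as a probable sarcopenia or fibromyalgia difference

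*Combined protocol and SAP*

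**What the plan says.** The title sets the aim: "Determination of Metabolomic Profile Differences in Sarcopenia Accompanying Fibromyalgia Syndrome". The opening section describes a cross-sectional observational study: "This study included 44 female patients aged 18-60 who were diagnosed with fibromyalgia", recruited from "outpatient clinics between May 2022 and December 2022 and 22 female healthy controls". The patients form two groups of 22 by one grip-strength cut-off: "patients with hand grip strength below 16 kg were considered to have probable sarcopenia". The controls are women who attended "outpatient clinics for other reasons and who did not have any accompanying diseases such as fibromyalgia and sarcopenia constituted the healthy controls". The 18-60 range is stated for the patients; none is stated separately for the controls.

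On possible confounders, the same section says "Demographic data, medication use and disease duration of the participants were recorded". It limits them by restriction only: women only (because sex may affect the metabolome), a list of excluded diseases, and exclusion for "use of systemic glucocorticoid, ACE inhibitor, angiotensin receptor blocker, statin, sulfonylurea".

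Selection of metabolites is described under Measurement of plasma metabolomics: "Two-tailed t-test was performed between experimental groups and significantly changed metabolites were identified". Pathway tools are named in the next sentence. The Statistical Analysis section adds a choice of parametric or non-parametric method according to normality, a comparison of the three groups, cluster and pathway analysis, and a 0.05 significance level. It names no covariate and no adjusted model.

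**The concern.** A t-test between self-formed groups answers only whether the groups differ. Grip strength defines the probable sarcopenia split, and one fixed cut-off across ages 18 to 60 does nothing to balance age between the two fibromyalgia groups. Controls do not have fibromyalgia, so their medication may differ from that of patients. Drugs outside the five excluded classes are not restricted.

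If age or a drug shifts a metabolite and also differs between groups, the t-test can flag that metabolite and a reader may credit the finding to probable sarcopenia or fibromyalgia. If the flagged metabolites are what enters the pathway analyses, which the order of the text suggests but does not state, the misattribution carries into the pathways. The plan accepts the principle for sex and for some drugs; it takes no comparable step for age within the range or for other medication, although the data are on file.

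**Working it through.** **No figure to reproduce.** The plan gives no effect size, SD, group ages, drug use by group or metabolite correlations. From the documents come only n = 22 per group, the two-tailed t-test and the 0.05 level. Everything else below is assumed, and each rate applies only to metabolites with the assumed dependence; that share is unknown.

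**Age, unadjusted test.** Let δ be the age gap in SD units and r the within-group age-metabolite correlation. With no group effect of its own, the metabolite still shows a standardised difference of r × δ. The t statistic has 2 × 22 − 2 = 42 degrees of freedom and noncentrality r × δ × √(22/2). For δ = 1.0 and r = 0.5 this is 0.5 × 3.317 = 1.66, giving a 36.7% chance of p<0.05.

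| Age gap | r = 0.1 | r = 0.2 | r = 0.3 | r = 0.5 |
|---|---|---|---|---|
| 0.25 SD | 5.1% | 5.3% | 5.7% | 6.9% |
| 0.5 SD | 5.3% | 6.2% | 7.7% | 12.8% |
| 1.0 SD | 6.2% | 9.9% | 16.3% | 36.7% |

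**Age in the model, linear effect.** Simulation over the same 12 cells (40,000 replicates each) gives 4.8% to 5.1%.

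**Age in the model, curved effect.** Assume metabolite = 0.3 × age + c × age², c from 0.1 to 0.3, residual SD 0.9, gap 0.5 or 1.0 SD. What a linear age term leaves depends on which group has the wider age spread:

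| Age spread | Unadjusted | Adjusted |
|---|---|---|
| Older group wider (SD ratio 1.5) | 15% to 56% | 6% to 14% |
| Older group narrower (SD ratio 0.67) | 5% to 27% | 5% to 7% |

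In the second row, at gap 0.5 SD and c = 0.3, adjustment is slightly worse than none (6.8% against 5.2%).

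**Drugs.** For an assumed drug shift of 0.1 to 0.8 SD, the unadjusted rate is about 5% to 11% with 60% against 30% use, and about 5% to 28% with 60% against 5% use. For 60% against 30%, modelling that drug gives about 5%, but only if the modelled class is the one causing the shift. Suppose instead that the commonest class is used by 60% in both groups, while another is used by 50% against 20% and shifts the metabolite by 0.8 SD. Adjusting for the commonest class then leaves the rate at about 11%, as before.

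**Scale.** Peak areas may be skewed. For log-normal data with an assumed log-SD of 1.0, a true shift of 0.8 SD on the log scale and no age gap, power is about 54% for a raw-scale age-adjusted model, 71% for Mann-Whitney and 73% for a log-scale age-adjusted model.

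**Cost of the age term.** The expected variance inflation for normally distributed age is 1 + (11δ² + 1)/40: 1.04, 1.09 and 1.30 for gaps of 0.25, 0.5 and 1.0 SD. Power for a true difference of 0.8 SD is 73.6% unadjusted. With age unrelated to the metabolite it falls to about 72%, 70% and 63%. With no age gap and r of 0.3 or 0.5 it rises to about 76% or 84%.

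**The case against.** The strongest reply is that the study is descriptive. It is cross-sectional, states no causal estimand, and an unadjusted contrast is a valid account of how the groups differ. Restriction by sex, disease and five drug classes already removes some confounding, and the exclusion list may not be exhaustive. Nothing shows an imbalance, and many cells in the table barely exceed 5%. The text is in the past tense, so changing the governing test may be a post hoc change rather than a matter of wording.

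Much of this stands. A reader might infer that the results are confounded, or that a rate near 37% is to be expected. The documents support neither: they give no group ages or drug use, and 37% is one corner of an assumed grid. Nor do they say that pathway input is limited to the selected metabolites. A reader might also infer that adjustment always helps; the curved-age results show that it need not. The post hoc point is fair and is met by labelling.

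The reply does not remove the point. The title ties the differences to sarcopenia accompanying fibromyalgia, restriction leaves age and other drugs open, and the choice between parametric and non-parametric tests concerns distribution, not confounding.

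**Conclusion.** The concern holds as a possibility that the plan leaves open. It is certain that selection is unadjusted and that no matching, stratification or covariate model is stated. Whether any bias exists, and its size, cannot be learned from the documents. The range of about 5% to 37% for age rests wholly on the assumed gaps and correlations, and the lower part of that range is negligible. Linear adjustment restores about 5% when the age effect is linear; with a curved effect and unequal age spread the remainder depends on direction, and adjustment usually but not always improves matters. Drug confounding can be only partly addressed between the two fibromyalgia groups, and not separated from disease where use is nearly confined to patients. This is a cheap improvement, not a flaw that invalidates the study.

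**What to change.** - For each pairwise comparison, fit a linear model per metabolite with group and age on log-transformed normalised peak areas, or on ranks where residuals remain clearly non-normal. This keeps the plan's provision for non-normal data.
- Let the age-adjusted result select metabolites and feed the pathway analyses, with the unadjusted test shown beside it. One test must govern: if either may select, the false-positive rate is 5.5% to 7.5% even with no age gap (r from 0 to 0.5).
- If the metabolite data have already been analysed, label the age-adjusted model post hoc, report both results, and state which metabolites change status.
- Tabulate age and each recorded drug class by group.
- For FMS PS+ against FMS PS-, add a sensitivity model with age plus the drug class whose use differs most between these two groups, chosen without looking at the metabolite results. State that it addresses only that class and that lost significance there alone does not show no difference.
- For fibromyalgia against control, state as a limitation that drug and disease effects cannot be separated where drug use is nearly confined to patients.
- Word results as associations.

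Cost: plan wording and analysis time, with no new participants or measurements, provided that age is among the demographic data. The age term takes one degree of freedom and inflates variance by about 4% to 30%, with the power changes shown above. The two-covariate sensitivity model inflates variance by about 7% to 45% under assumed drug use of 40% in both groups up to 60% against 30%, with power for 0.8 SD of about 71% down to 58%.

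### The plan names no global test of a metabolomic profile difference and no multiplicity control for its metabolite t-tests, and cluster analysis cannot fill that gap.

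*Combined protocol and SAP*

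**What the plan says.** The official title states the aim: "Determination of Metabolomic Profile Differences in Sarcopenia Accompanying Fibromyalgia Syndrome". No hypothesis, primary contrast or rule for concluding that a profile differs follows from it. The opening section gives 22 women with fibromyalgia and probable sarcopenia (PS+), 22 with fibromyalgia alone (PS-) and 22 healthy controls.

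The metabolome analyses are described in two places.

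- *Measurement of plasma metabolomics*: "Two-tailed t-test was performed between experimental groups and significantly changed metabolites were identified". Then: "Metaboanalyst 4.0 platform and KEGG (Kyoto Encyclopedia of Genes and Genomes) database were used in pathway analyses". No test or threshold is given for the pathway step.
- *Statistical Analysis*: after a normality check, "statistical evaluation was made with appropriate parametric or non-parametric tests". For the metabolome: "After comparing the metabolome data between the three groups, cluster analysis was performed and pathway differences between the groups were revealed". The method of the three-group comparison, the clustering algorithm and the variables entering the clustering are not stated. On the error rate: "The results were evaluated at the 95% confidence interval and the significance level was $p<0.05".

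Neither section mentions an adjustment for the number of metabolites or contrasts. The work is untargeted, and the number of accepted metabolites is not given.

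**The concern.** A statement that the profile differs between groups needs a procedure with a known chance of making that statement when it is false. The plan offers two candidates by name.

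The first is the set of single-metabolite t-tests. These are genuine tests, but with many of them at an unadjusted p<0.05, some metabolite will usually look changed when nothing is.

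The second is cluster analysis. It partitions any data it is given and attaches no error rate to a difference between PS+ and PS-. If it is run on metabolites already selected for p<0.05, it will tend to echo the grouping that did the selecting.

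The headline conclusion would then have no known false-positive rate. There is also a risk in the other direction: modest shifts spread over many metabolites can be missed one metabolite at a time, and no named method looks for them jointly.

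**Working it through.** **Starting point.** The documents give no sample-size calculation, power, effect size or standard deviation, so there is no figure of the plan's to reproduce.

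**Inputs from the documents.** Groups of 22, 22 and 22; two-sided tests; significance level 0.05; no stated adjustment.

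**Assumptions.** One t-test per metabolite per pair of groups; number of metabolites m from 20 to 300; correlation between metabolites as stated below.

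**1. Unadjusted t-tests with no true difference.** Under independence, the chance of at least one p<0.05 in a contrast is 1 - 0.95^m, and the expected number is 0.05 × m.

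| m | At least one p<0.05 | Expected, one contrast | Expected, three contrasts |
|---|---|---|---|
| 20 | 64.2% | 1 | 3 |
| 50 | 92.3% | 2.5 | 7.5 |
| 100 | 99.4% | 5 | 15 |
| 200 | over 99.9% | 10 | 30 |
| 300 | over 99.9% | 15 | 45 |

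Correlation lowers the first column but does not rescue it. In simulation (22 vs 22, 400 runs, correlation 0.3 among all metabolites) it is 80.5% at m = 50 and 92.2% at m = 100.

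**2. Clustering with no true difference.** In the same simulation, with correlation 0 and 0.3, Ward clustering cut at two returned two clusters in 100% of runs. Agreement with the real groups, labelling the clusters whichever way fits better, averaged about 56%. When only metabolites with p<0.05 were clustered (an assumption about practice), it rose to 65-68%.

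**3. Do the candidate repairs hold the error rate?** With no true difference:

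- Bonferroni-adjusted t-tests: 1 - (1 - 0.05/m)^m = 4.9% for m from 20 to 300; 3.5-7.2% in simulation.
- Benjamini-Hochberg at 5%: any discovery is then a false one. Simulated with metabolites in correlated blocks, 3-6% of studies had one.
- Permutation test on the whole profile: 4.0-5.5% with a common correlation; 3-7% with correlated blocks.

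All are consistent with 5%, given that the Monte Carlo standard error at 400 runs is √(0.05 × 0.95 / 400) = 1.1 percentage points.

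**4. Which repair detects more?** Simulated power with m = 100 in blocks of 10, 22 vs 22, 400 studies per setting, at within-block correlation 0 / 0.3 / 0.5:

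| Assumed pattern | Global permutation test | Any discovery at 5% FDR |
|---|---|---|
| 20% shifted by 0.5 SD | 91 / 78 / 57% | 45 / 44 / 45% |
| 30% shifted by 0.4 SD | 93 / 72 / 53% | 38 / 36 / 32% |
| 30% shifted by 0.5 SD | 99 / 98 / 88% | 62 / 59 / 63% |
| 10% shifted by 0.8 SD | 98 / 87 / 65% | 85 / 84 / 87% |

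The ranking is not fixed:

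- With 5% shifted by 1.0 SD and 50-100 metabolites, the global test has 18-89% against 65-92%.
- With m = 50, block correlation 0.5 and 20% shifted by 0.5 SD, it has 30% against 39%.
- With m = 100, a common correlation of 0.3 and 20% shifted by 0.6 SD, it has 28% against 48% for Bonferroni.

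So neither analysis replaces the other.

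**The case against.** The strongest reply is that the t-tests are inferential, and that adjusting them would alone give a valid answer. Step 3 bears this out. A reader might infer that clustering is what deprives the study of a valid yes/no answer. The documents do not support that: the missing multiplicity control does at least as much of the damage, and a global test is one of two sound repairs. What remains is that the plan states neither.

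A reader might also infer that nothing beyond t-tests and clustering was done. The text does not show this. It reports a three-group comparison, refers to suitable parametric or non-parametric tests, and includes a pathway step that combines metabolites. These are under-specified rather than shown to be absent, but a method that is not named cannot serve as the specified test.

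The title can also be read as descriptive: find which metabolites and pathways differ. No yes/no hypothesis is written down, nor any intention to judge a difference from a cluster picture, and the documents do not define a profile as many small shifts. Even so, the plan sets a significance level and speaks of significant changes and of differences revealed, so it makes inferential claims and needs a rule for them.

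Finally, the power comparison rests on assumed patterns, and the documents do not say whether diffuse or sparse differences are likelier. This rules out making the global test the sole gateway to any claim. It does not remove the case for adding it.

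**Conclusion.** The point holds in this form: the plan names no global test of a profile difference and states no multiplicity control for its metabolite t-tests, and clustering cannot stand in for either. Followed as written, the chance of at least one nominally significant metabolite per contrast with no true difference is about 64% at 20 metabolites, 92% at 50 and over 99% at 100. These figures assume independence and an unstated metabolite count; with a correlation of 0.3 they fall to about 81% at 50 and 92% at 100.

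This is a worthwhile, inexpensive improvement. It is not evidence that no valid analysis was carried out. The false-positive argument is firm across the assumed range of metabolite counts. The power argument for the global test is conditional on differences being spread over many metabolites and on how the metabolites correlate.

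**What to change.** Amend *Statistical Analysis* as follows.

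1. **Whole-profile test.** Permutation multivariate analysis of variance on Euclidean distances of log-transformed, autoscaled values of all accepted metabolites, with 9,999 label permutations. PS+ vs PS- comes first and PS- vs control second. Report R-squared and p for each.
2. **Metabolite tests.** Keep the two-tailed t-tests, with false-discovery-rate adjustment across metabolites. State how many metabolites were tested.
3. **Claims.** Claim an overall profile shift only from the global test. Claim differences in named metabolites from the adjusted t-tests, even when the global test is not significant.
4. **Clustering.** Label it descriptive and state which metabolites entered it.
5. **Three-group comparison.** Name its method.

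The cost is a few sentences and minutes of computing on the existing peak table, with no new samples. There are three downsides. The global test is less sensitive than adjusted single tests when few metabolites differ strongly, and in some correlated settings even for diffuse shifts. The headline may become negative. And since patients were recruited from May to December 2022 and the document is dated January 25, 2023, the test should be reported as specified after data collection.
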